### **4. Statistical Plan**

*Statistical analysis:* Categorical variables will be presented as n/N (%) with 95% confidence intervals. Continuous variables will be presented as mean +/-SD or median [range]. A Pearson's chi-square test or Fisher exact test will be used for frequencies and proportions of categorical values and t test or the non-parametric Wilcoxon rank sum test for mean values of continuously measured variables. P values  $\leq 0.05$  will be considered statistically significant and we will use SAS (version 9.4, The SAS Institute, Cary NC) as our statistical package to perform these analyses. The primary investigator will perform the statistical analysis with assistance from the WHI statistician.

We will use data from a historical control group discharged on POD 1 after minimally invasive sacrocolpopexy to examine Aim 1 and Aim 2. This is a cohort of 60 women matching our eligibility criteria from a prospective randomized trial of two different types of lightweight polypropylene mesh (IRB #14-354). This study completed recruitment 2017. It consists of a group of women who underwent minimally invasive sacrocolpopexy using the same surgical approaches, at the same institutions (main campus, Fairview and Hillcrest), and performed by the same surgeons as our study. The primary difference is that participants in that study and the cohort proposed here is that all participants were discharged home on POD 1. We will utilize this cohort to compare the incidence and severity of procedure-related adverse events and costs between SDD and POD 1. Comparisons on outcome measures will be done using either an ANOVA analysis or a student's t test for parametric continuous outcomes, a Kruskal-Wallis or Mann Whitney U test for non-parametric outcomes and a Chi-square test for all categorical outcomes. Logistic regression will be performed to control for confounding variables.

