*Sample size:* We estimate that approximately 80 minimally invasive sacrocolpopexy surgeries will be performed per year. Of these, we anticipate that ~3/4 will meet eligibility criteria and of these patients, ~3/4 will consent to participate. Based upon data by Unger et al, a Clavien Dindo grade 3 adverse event (defined as requiring surgical, endoscopic, or radiologic imaging/intervention) was identified in 26.3% of patients after a minimally invasive sacrocolpopexy. A meta-analysis of laparoscopic versus open sacrocolpopexy combined results of 9 randomized control-trials and found a post-operative complication rate of 5.4% after minimally invasive sacrocolpopexy (robotic and laparoscopic). We suspect that 26.3% may be an overestimation of adverse events as the Unger et al study included any imaging required in the postoperative period even if the result was normal. However, we also suspect that a 5.4% adverse event incidence may be low. As such, we feel that an adverse event incidence of 12% may be more representative of that expected after this surgical procedure.

We used a one-sided exact test for non-inferiority of binomial proportion to determine the degree of difference between the proportion of 26.3% and an incidence proportion greater than the reference which could be detected and deemed inferior (significantly greater) to the reference with a power of 80%. With a sample size of 45 patients, the proportion of patients with a Clavien Dindo grade of 3 will need to be 45.1% or greater. We will account for a 3% drop out rate (based on 2016 post-operative visit "no-show" rates for the Urogynecology division) by recruiting an additional 2 patients, making the sample size planned for this study a total of 47 patients.

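### The adjusted comparison with historical controls rests on logistic regression with few expected events (about 13 at the plan's 12%) and no sparse-data method; a Firth penalty and a short covariate list would make it steadier at little cost

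*Combined protocol and SAP*

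**What the plan says.** Section 4 (Statistical Plan) compares adverse events and costs with a historical group discharged on the first postoperative day: "This is a cohort of 60 women matching our eligibility criteria from a prospective randomized trial". Categorical outcomes are to be compared by chi-square test, and Fisher's exact test is also available. Adjustment is covered by one sentence: "Logistic regression will be performed to control for confounding variables". The section does not say which outcome is modelled, which confounders enter, how many there are, or what happens if events are few.

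The sample-size paragraph fixes the evaluable group ("With a sample size of 45 patients, the proportion of patients with a Clavien Dindo grade of 3 will need to be 45.1% or greater") and the number recruited ("recruiting an additional 2 patients, making the sample size planned for this study a total of 47 patients"). It mentions three event rates:
- 26.3%, the design reference, which the investigators suspect is too high because it counted imaging with normal results.
- 5.4%, from a meta-analysis that "found a post-operative complication rate of 5.4% after minimally invasive sacrocolpopexy", which they suspect is too low.
- 12%, their own judgement: "we feel that an adverse event incidence of 12% may be more representative".

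Section 3 (Data Collection) defines a serious adverse event as Clavien-Dindo grade 3 or higher. It sets the decision rule by comparing the proportion with 26.3% and a 45.1% cut-off.

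**The concern.** The two cohorts were not randomised and come from different periods, so the adjusted odds ratio is the plan's analytic answer to remaining case-mix differences in Aim 1. Logistic regression fitted by maximum likelihood behaves poorly when there are only a few events per model term. Estimates scatter widely, a real effect is exaggerated on average, and in the sparsest data a coefficient can run off to infinity. The plan provides a small-sample test for crude comparisons but nothing equivalent for the adjusted one. At stake is whether that adjusted odds ratio can be trusted, in a comparison meant to show that same-day discharge is no less safe.

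**Working it through.** **Inputs.** 45 evaluable women, 60 controls, and rates of 5.4%, 12% and 26.3% (all from section 4). Applying one rate to both cohorts is an assumption, and it matches the Aim 1 hypothesis of no difference.

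**1. The plan's own figure.** Exact one-sided binomial test, n = 45, reference 0.263:
- P(X ≥ 17) = 0.061 and P(X ≥ 18) = 0.031, so the critical count at 0.05 is 18.
- P(X ≥ 18 at 0.451) = 0.798, so the stated 45.1% at 80% power is reproduced. The sample-size paragraph gives no alpha; 0.025 would give only 70.3%.
- 45 / 0.97 = 46.4, which rounds up to 47.

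This calculation uses the same-day-discharge proportion alone. No regression enters it.

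**2. Expected events in 45 + 60 = 105 women, and events per model term.** The terms are cohort plus the covariates.

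| Rate | Events (45 + 60) | Per term, 3 covariates (÷4) | Per term, 8 covariates (÷9) |
|---|---|---|---|
| 5.4% | 2.4 + 3.2 = 5.7 | 1.4 | 0.6 |
| 12% | 5.4 + 7.2 = 12.6 | 3.2 | 1.4 |
| 26.3% | 11.8 + 15.8 = 27.6 | 6.9 | 3.1 |

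**3. Chance that one cohort has no event**, so that even the crude odds ratio cannot be estimated: 1 − [1 − (1−p)^45] × [1 − (1−p)^60]. This is 11.5% at 5.4%, 0.36% at 12% and practically nil at 26.3%.

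**4. Simulation of the adjusted model.** There were 2,000 data sets per setting, each with 45 v 60 women. Covariates alternated between continuous (0.2 SD imbalance) and binary (30% v 40%), each with odds ratio 1.5. The overall event rate was held at the stated value, and the true cohort odds ratio was 0.5, 2 or 3. These covariate settings are assumptions, because the plan gives none. The mean log odds ratios (SD) below are for a true odds ratio of 2 (log 0.693). The failure column gives the range over all three odds ratios.

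| Rate | Covariates | No maximum-likelihood estimate | Maximum likelihood | Firth |
|---|---|---|---|---|
| 5.4% | 3 | 21-26% | 0.652 (0.92) | 0.691 (0.95) |
| 5.4% | 8 | 40-48% | 0.732 (1.26) | 0.623 (1.01) |
| 12% | 3 | 1-2% | 0.746 (0.76) | 0.688 (0.69) |
| 12% | 8 | 2-5% | 0.896 (0.93) | 0.723 (0.73) |
| 26.3% | 3 | 0% | 0.738 (0.52) | 0.697 (0.49) |
| 26.3% | 8 | 0% | 0.797 (0.64) | 0.698 (0.55) |

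The maximum-likelihood columns use only data sets that gave an estimate. At 5.4% the extreme ones drop out, so those means show no consistent bias and flatter the method. Other covariate assumptions brought the failure rate at 5.4% down to about 7%.

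**5. Bias.** Over the three odds ratios at 12%, maximum likelihood overshoots the log odds ratio by 8-11% with 3 covariates (for example 0.746 / 0.693 = 1.08) and by 21-29% with 8 (0.896 / 0.693 = 1.29). At 26.3% the overshoot is 7-9% and 15-20%. With a true odds ratio of 1, no bias was seen beyond simulation error.

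**6. Total error.** Root mean square error = √(bias² + SD²), at 12% and odds ratio 2:
- 3 covariates: √(0.053² + 0.76²) = 0.76 by maximum likelihood, against 0.69 by Firth.
- 8 covariates: √(0.203² + 0.93²) = 0.95, against √(0.030² + 0.73²) = 0.73.

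The gain is not confined to a true difference. With a true odds ratio of 1, a 26.3% rate and 6 covariates, the error was 0.59 by maximum likelihood and 0.53 by Firth.

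**7. What remains.** At 12% with 3 covariates, a 95% interval extends by a factor of about exp(1.96 × 0.76) = 4.4 either way by maximum likelihood, and exp(1.96 × 0.69) = 3.9 by Firth.

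**The case against.** The strongest reply is that the plan is under-specified, not wrong. Its sentence names no outcome and no estimation method. Firth's penalty is an option within the same SAS procedure, a statistician is involved, and the model might be meant for commoner outcomes such as patient calls or unscheduled visits. That stands in part: reading the sentence as maximum likelihood applied to serious events is an inference, although it is the usual meaning.

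Four stronger readings are tempting, and the documents do not support them.
- *The odds ratio is biased as planned.* Aim 1 hypothesises no difference, and at a true odds ratio of 1 there is no bias, only scatter. With 3 covariates at 12%, the mean corresponds to an odds ratio of about 2.1 instead of 2.0, which is small beside the interval.
- *The model will often fail.* That applies near 5.4%, a rate the plan thinks too low and which is a general complication rate, not a grade 3 rate. At 12% failure is uncommon.
- *Only 6 to 13 events are possible.* The plan doubts 26.3% but designs on it, and its own description of grade 3 mentions imaging. About 28 events cannot be ruled out.
- *The trial's conclusion, or all protection against confounding, depends on this model.* The decision rule does not use it. The controls are also described as meeting the same eligibility criteria, with the same surgeons, institutions and approaches.

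**Conclusion.** The point holds as a cheap improvement to the adjusted historical-control comparison. It is not a flaw in the decision rule. With about 13 serious events expected at 12% (about 6 at 5.4%, about 28 at 26.3%), maximum-likelihood logistic regression with several confounders gives an unstable odds ratio. It exaggerates a true difference modestly with 3 covariates and materially with 8. Near 5.4%, it may give no estimate in about 7-48% of data sets. At 12%, Firth's penalty lowers total error from 0.76 to 0.69 with 3 covariates and from 0.95 to 0.73 with 8.

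The event counts follow directly from the plan. The bias, failure and error figures depend on the assumed number, strength and imbalance of covariates. Small numbers remain the larger limit under either method.

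**What to change.** In section 4, replace the single sentence on adjustment with a statement that:
- adjusted comparisons of serious adverse events and other infrequent binary outcomes will use Firth penalised logistic regression (the FIRTH option in SAS PROC LOGISTIC) with profile-likelihood confidence intervals;
- the model will contain cohort and a short list of pre-operative confounders, named before the outcome data are examined.

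A single propensity score for cohort membership, built from those confounders, is an acceptable alternative to separate covariates but is not required. In runs with six covariates and a true log odds ratio of 0.69, it gave means of 0.66 and 0.68, slightly towards no difference.

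The cost is a sentence or two and one option in software already chosen, with no extra patients. The downside is slight shrinkage towards no difference in the sparsest settings: at 5.4% with 8 covariates and odds ratio 2, the Firth mean was 0.623 against 0.693, about 10%. That direction matters in a safety comparison and is a further reason to keep the list short. The report should also say plainly that the interval remains wide, since the penalty does not make up for few events.

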### **Research Plan**

#### **1. Study Design**

This is a prospective cohort study evaluating safety, cost and patient satisfaction with SDD for patients undergoing minimally invasive sacrocolpopexy for pelvic organ prolapse. A prospectively collected, historical control group who underwent the same surgical procedure will be utilized to compare these outcomes when applicable. SDD will be facilitated in part by a utilizing novel patient education video created for this study and implementing an ERAS pathway. All patients meeting eligibility criteria will be approached for study participation. Outcomes will be assessed on POD 0/1 and at the routine post-operative follow up visit, generally at 6 weeks after surgery.

**Primary outcomes:** The primary outcome of this study is serious adverse events.

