### **3. Data Collection**

The EMR will be reviewed to collect preoperative, intraoperative, and POD 0 data points. We will use the following method to identify the occurrence of a procedure-related adverse event: The EMR will be reviewed for patient phone calls for a procedure-related complication, unscheduled office visits, emergency department visits, hospital readmissions or reoperations within 30 days, and adverse events occurring up to 6 weeks post-operatively. The adverse events of interest will include the following:

- Wound infection
- Hematoma
- Transfusion
- Pelvic abscess
- Osteomyelitis
- Venous thromboembolism (deep vein thrombosis or pulmonary embolism)
- Delayed bowel or urinary tract injury
- Bowel obstruction or ileus
- Cardiac or pulmonary complication
- Neurologic injury

We will also employ an approach that will allow us to capture events that may have been handled outside of the CCHS or in institutions that do not utilize *Epic*. To capture these data points if they exist, we will contact participants by telephone on POD 1 (within 24 hours of surgical completion time) to determine if they received any care from a facility outside of the CCHS and then again at the post-operative follow up visit, which generally occurs at 6 weeks. We will then use these data with the Clavien Dindo Scale to determine the severity of the adverse event, with a grade 3 or higher considered to be a serious adverse event, and we will compare this proportion to the reference proportion of 26.3%. A proportion of patients with grade 3 or higher less than 45.1% will be considered non-inferior to the reference.

As part of the effort to characterize the patient population, we will extract data regarding total procedure-related costs using the EMR. We will assess satisfaction using the quality of recovery questionnaire, visual analog scores for postoperative pain, and a patient satisfaction survey described by Fountain et al at the postoperative visit, which uses a Press Ganey scale for responses (See Appendix A). Please see data collection sheet for a comprehensive list of planned data points.

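### The primary outcome has no rule on imaging, yet it is compared with a 26.3% reference that counted imaging even when normal

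*Combined protocol and SAP*

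**What the plan says.** Section 1 (Study Design) states: "The primary outcome of this study is serious adverse events". Section 3 (Data Collection) makes this operational by grading events on the Clavien Dindo Scale, "with a grade 3 or higher considered to be a serious adverse event". It compares the proportion with 26.3% and gives the decision rule: "A proportion of patients with grade 3 or higher less than 45.1% will be considered non-inferior to the reference". The section does not mention imaging, and the grades of the scale are not set out anywhere.

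The Sample size paragraph of Section 4 (Statistical Plan) gives the origin of the 26.3%. In a cited study of adverse events after this operation, a grade 3 event, "defined as requiring surgical, endoscopic, or radiologic imaging/intervention", "was identified in 26.3% of patients after a minimally invasive sacrocolpopexy". The authors suspect this is too high because the study "included any imaging required in the postoperative period even if the result was normal". They conclude that "we feel that an adverse event incidence of 12% may be more representative of that expected after this surgical procedure", but keep 26.3% as the reference. For this trial's own 45 patients the paragraph then says that "the proportion of patients with a Clavien Dindo grade of 3 will need to be 45.1% or greater", without mention of grades above 3.

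Section 4 also plans to compare the incidence and severity of adverse events with 60 women from an earlier mesh trial who went home on postoperative day 1.

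**The concern.** A one-sample comparison with a fixed reference is meaningful only if the trial counts events as the reference did. Here the reference includes women whose only qualifying item was a scan, possibly a normal one, and the plan does not say whether such women count in the SDD cohort. Two assessors could class the same woman differently, and the choice could be made after the charts have been read.

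Both choices cause trouble. Leaving imaging out lowers the SDD proportion relative to 26.3% without any difference in harm. Counting it turns a normal scan into a serious adverse event in the primary safety result. The comparison with the 60 controls is exposed to the same gap, because no common imaging rule is stated for the two cohorts.

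**Working it through.** **1. Reproduce the plan's figure.** Inputs from Section 4: n = 45, reference p0 = 0.263, one-sided exact binomial test, 80% power, 3% dropout. The significance level for this test is not given separately. I take one-sided 0.05, matching the general level in Section 4.

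- Smallest r with P(X ≥ r | 45, 0.263) ≤ 0.05: r = 18, where the tail is 0.031.
- Solve P(X ≥ 18 | 45, p1) = 0.80: p1 = 45.15%. Power at 45.1% is 79.8%.
- Variants fit less well: one-sided 0.025 gives 47.4%, one-sided 0.10 gives 42.9%, and the normal approximation at 0.05 gives 43.3%.
- Dropout: 45 / 0.97 = 46.4, rounded up to 47.

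Both 45.1% and 47 reproduce. The cut-off is derived from 26.3%, so it carries the imaging-inclusive counting of that figure.

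**2. Set the counting rules side by side.**

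| Quantity | Where | Grades | Imaging alone |
|---|---|---|---|
| Trial outcome and decision rule | Section 3 | 3 or higher | not stated |
| Reference 26.3% | Section 4, Sample size | 3 | counted, even if normal |
| 45.1% for this trial's patients | Section 4, Sample size | 3 | not stated |
| 60 controls | Section 4, Statistical analysis | severity compared | not stated |

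Read literally, a woman whose worst event is above grade 3 counts under Section 3 but not under the sample-size sentence.

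**3. Direction of the mismatch.** Write the reference as a + b, where a is the proportion with a qualifying event other than imaging alone and b the proportion with imaging alone, so a + b = 26.3%. If the SDD cohort has the same underlying experience but imaging alone is left out, its expected proportion is a. The expected difference from the reference is then a − (a + b) = −b, which favours SDD whenever b > 0.

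**4. Possible size.** The documents do not give b. Under assumptions:

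- b = 0: no shift.
- a = 12% (the authors' judgement, assumed here to be the rate without imaging): b = 26.3 − 12 = 14.3 points. In 45 women that is 11.8 against 5.4, a gap of 0.143 × 45 = 6.4.
- a = 5.4% (the meta-analysis complication rate, a different outcome): b = 26.3 − 5.4 = 20.9 points, or 0.209 × 45 = 9.4 women.

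These values illustrate scale. They do not estimate the effect of imaging.

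**5. Consequence for the decision rule.** A proportion below 45.1% means at most 20 of 45 (20/45 = 44.4%; 21/45 = 46.7%).

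- Counts near the two expected values both pass: 12/45 = 26.7% (exact 95% interval 14.6% to 41.9%) and 5/45 = 11.1% (3.7% to 24.1%).
- P(X ≤ 20 | 45, 0.263) = 99.7%. If the rate without imaging were 12% (assumption), a true rate of 26.3% would be 26.3 / 12 = 2.2 times that rate and would still almost always be called non-inferior.
- Repeating the calculation in step 1 with a 12% reference gives r = 10 and a detectable proportion of 26.7%. With 5.4% it gives r = 6 and 17.0%.

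**The case against.** The strongest reply is that the trial's outcome is defined once, in Section 3, and that the imaging wording merely reports a cited study whose count the authors then question. That stands. A reader might infer two rival definitions of the trial's own outcome, but the documents do not support this. Omitting the higher grades from the sample-size sentence is probably shorthand, since Section 3 attaches the same 45.1% to grade 3 or higher.

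It can also be said that Section 3 grades adverse events from a list that contains no normal scan, so imaging alone would not be graded at all. This is a natural reading, but it leads directly to the unlike comparison, a count without imaging against a reference with it. The data collection sheet might hold a grading rule, but it is not among the documents reviewed.

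Three further inferences go too far.

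- That about six women change class because of imaging. The 12% is a judgement placed between 26.3% and 5.4%, and the protocol does not present it as the rate without imaging.
- That SDD women would be scanned more often than controls. Nothing in the documents says so, and the controls went home on day 1, so nearly all of the six-week follow-up is outside hospital in both cohorts.
- That the controls are not tied to any grading. Aim 1 names the scale and the historical comparison, and Section 4 compares severity. Only the imaging rule is missing.

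Finally, the illustrative counts of 12 and 5 both pass the stated rule, so the choice of definition does not by itself reverse the decision at those values. That also stands. The effect is on what the comparison means and on the reported safety proportion.

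**Conclusion.** The concern holds as a mismatch between outcome and reference. Followed as written, the plan can set an SDD proportion without imaging against a 26.3% that includes it, and against a 45.1% cut-off built on that figure. The bias then favours SDD by the imaging-only share of the reference. The documents do not give that share. It is 14.3 points if the authors' 12% is taken as the rate without imaging, which is an assumption. The missing shared rule for the controls and the inconsistent grade wording are smaller parts of the same gap.

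This is not an error in the sample-size arithmetic. The conclusion also does not depend on what the published scale says about imaging, which cannot be checked from the documents. It should be corrected before any chart is graded.

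**What to change.** In Section 3, before charts are graded, state one rule: a serious adverse event is Clavien Dindo grade 3 or higher; every event above grade 3 counts; and a grade 3 event needs a surgical, endoscopic or radiologic intervention, so diagnostic imaging alone does not count. The intervention condition must apply to grade 3 only. Otherwise a severe cardiac or pulmonary complication managed without a procedure would drop out. Excluding imaging is a choice, since the documents do not set out the grades. What matters is that it is written down and applied to everyone.

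Then:

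- Grade the SDD women and the 60 controls by this rule, and compare the imaging-exclusive proportions between the cohorts.
- Add a yes/no field for imaging-only events in both cohorts. Report an imaging-inclusive count, and set only that count against 26.3% and 45.1%.
- Change the sample-size sentence in Section 4 to grade 3 or higher.

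The cost is protocol wording, one data field and regrading of the control charts. N = 47 does not change while 26.3% remains the reference for the imaging-inclusive count. That number was derived for the comparison with 26.3%, not for the comparison with the controls, so the latter should be reported with its confidence interval.

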#### Post-operative Follow-up

- POD 0: All patients will be contacted by an individual on their surgical team to see how the patient is doing. If patients have a late discharge from the hospital, after 1700, a POD0 call will not be initiated. This call will last approximately 5 minutes in length (or as dictated by patient questions or concerns), to occur between 1500 and 1900 on day of surgery.
- POD 1: All patients will be contacted within 24 hours of their surgical completion time by a registered nurse or a physician. This call will last approximately 10 minutes in length.
- All patients will have a scheduled post-operative visit at ~6 weeks, as per our standard protocol.

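### Women who miss the 6-week visit are budgeted as drop-outs although the primary outcome comes mainly from the EMR, and no later contact asks them about care received elsewhere

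*Combined protocol and SAP*

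**What the plan says.** Four parts of the combined protocol and SAP bear on this.

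- **Section 4, Sample size.** The calculation rests on 45 women ("With a sample size of 45 patients"). The allowance for loss is then set from visit attendance: "We will account for a 3% drop out rate (based on 2016 post-operative visit" no-show rates in the Urogynecology division). Two women are added, "making the sample size planned for this study a total of 47 patients".
- **Section 3, Data Collection.** The EMR is reviewed for complication calls, unscheduled and emergency visits, readmissions or reoperations to 30 days, and adverse events to 6 weeks. Events are graded on the Clavien-Dindo scale, and grade 3 or higher counts as serious. To find care given outside the health system, women are asked on POD 1 and "then again at the post-operative follow up visit, which generally occurs at 6 weeks".
- **Paradigm, Post-operative Follow-up.** The POD 1 contact is early: "All patients will be contacted within 24 hours of their surgical completion time by a registered nurse or a physician". The only other call is on the day of surgery. The next scheduled contact is the visit at about 6 weeks.
- **Specific Aims, Aim 1.** Telephone calls are to be used to ask about outside events, with no timing given.

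The plan gives no analysis set or denominator for the primary proportion, no missing-data rule, and no fallback contact after a missed visit.

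**The concern.** The sample-size paragraph and the data-collection section imply different evaluable sets. An allowance based on visit no-shows makes sense only if a woman who misses the visit contributes nothing to the primary proportion. Under Section 3, most of what that proportion needs is in her record whether or not she attends.

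The real loss for a non-attender is narrower. She is asked about outside care once, within 24 hours of surgery, and not again. Several of the listed events, such as pelvic abscess, osteomyelitis, thromboembolism and delayed bowel or urinary tract injury, would mostly present later than that. If such an event is treated at a hospital whose records the study cannot see, the plan as written has no means of learning of it. This falls short of what Aim 1 promises.

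Two errors are possible, and they are alternatives for any one woman:

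- **Kept on EMR data alone.** Her outside events count as none. This can only lower the measured rate.
- **Excluded.** Any event already in her EMR is lost. The direction then depends on how her group's event rate compares with that of attenders.

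Safety is the primary outcome and wide use of same-day discharge is the stated goal, so under-recording of serious events deserves closing off. The information is hard to recover once the follow-up window has passed.

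**Working it through.** **Inputs.** From Section 4: 45 evaluable women, 3% drop-out, 47 planned, reference 26.3%, 80% power, expected incidence 12%, general significance level 0.05. From Section 3: non-inferiority limit 45.1%.

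**1. The plan's own figures.**
- Inflation: 45 / (1 − 0.03) = 46.4, rounded up to 47. This matches.
- Exact one-sided binomial test, n = 45, p0 = 0.263, alpha 0.05: reject at 18 or more events (exact size 0.031). Power at 45.1% is 79.8%, and the proportion detectable with 80% power is 45.15%. This matches the stated 45.1%. At one-sided 0.025 it would be 47.4%, so 0.05 was used.

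No number in the plan is wrong on this point.

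**2. How many women.** Expected non-attenders are 47 × 0.03 = 1.4, and the plan allows for 2. If attendance is independent between women, the chance of 3 or more at a 3% rate is 16.7%.

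**3. Effect on the proportion with 2 non-attenders.** Let x be the number of attenders with an event.

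| x | Attenders only, x/45 | All 47, both non-attenders event-free, x/47 | All 47, both with an event, (x+2)/47 |
|---|---|---|---|
| 5 | 11.1% | 10.6% | 14.9% |
| 6 | 13.3% | 12.8% | 17.0% |
| 12 | 26.7% | 25.5% | 29.8% |
| 20 | 44.4% | 42.6% | 46.8% |

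- Excluding non-attenders: the worst understatement at x = 5 is 14.9 − 11.1 = 3.8 points. If both are event-free, exclusion overstates the rate by 11.1 − 10.6 = 0.5 points.
- Keeping them with outside events missed: the understatement is at most 2/47 = 4.3 points.

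**4. How likely the extreme is.** At the plan's 12% for each woman, two non-attenders have 2 × 0.12 = 0.24 expected events. The chance that both have one is 0.12² = 1.4%, if they carry the same risk as others and are independent.

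**5. Effect on the decision against 45.1%.** The largest passing count is 20 of 45 (44.4%), 20 of 46 (43.5%) or 21 of 47 (44.7%).
- Two excluded, both with events: only x = 20 changes, from 20/45 (pass) to 22/47 = 46.8% (fail).
- One excluded with an event: 20/46 becomes 21/47 = 44.7%, still a pass, so nothing changes.
- Two kept, both with missed events: only recorded counts of 20 or 21 of 47 change, to 22/47 or 23/47 = 48.9%.

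**6. A higher no-show rate.** The 3% comes from the Urogynecology division, while Female Urology also enrols. As an assumption with no source in the documents, take 10%: 47 × 0.10 = 4.7, about 5 women. The worst case is then 5/42 = 11.9% becoming 10/47 = 21.3%, or 9.4 points. The decision would change only if at least 17 of 42 attenders (40.5%) already had events, since 17 + 5 = 22.

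**The case against.** The strongest reply is that the no-show rate is used once, in advance, to inflate a sample size. It does not define an analysis population. EMR review in Section 3 is not conditional on attendance, so the natural reading is that a non-attender with a recorded event counts. Aim 1 mentions telephone calls about outside care without limiting them to POD 1. The plan's own rate concerns one or two women, and even the worst cases of 14.9% and 21.3% lie below both the 26.3% reference and the 45.1% limit.

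Much of this stands, and it rules out three stronger readings:

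- **That non-attenders are removed from the safety proportion or replaced.** No text says so. Recruiting two extra women at the outset is inflation, not replacement. Exclusion is only an implication of how the allowance was built.
- **That non-attenders are the women most likely to have been treated elsewhere.** This is plausible, but nothing in the documents supports it. The 3% is a general divisional figure with no link to complications.
- **That every route favours same-day discharge.** Dropping event-free women raises the proportion (5/45 = 11.1% against 5/47 = 10.6%).

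The reply does not close the gap in capture. Aim 1 gives no timing, and neither Section 3 nor the follow-up schedule contains a call after POD 1. A woman followed exactly as written who misses the visit is never asked about late outside events, and no rule says how she enters the proportion.

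**Conclusion.** The point holds as a minor one. The drop-out allowance implies that non-attenders are not evaluable, which does not fit a primary outcome read mainly from the EMR, and the outside-care question is not asked of them after the first 24 hours.

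At the plan's 3%, the effect is confined to 1 or 2 women and at most about 4 percentage points. The primary decision does not change at the expected 12%. It could change only when the observed count is already next to the limit. The reported rate and its 95% confidence interval are more exposed than the decision, because two missed events beside about five recorded ones is not a trivial share.

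This rests on the 3% rate holding across both recruiting services, and the bounds assume that every non-attender had a serious event. A reader might infer deliberate or systematic removal of complicated cases; the documents do not support that. What is missing is a rule and a contact.

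**What to change.** 1. **Denominator (Sections 3 and 4).** State that every eligible enrolled woman who had the surgery stays in the primary proportion, using EMR data through 6 weeks, whether or not she attends. Reconcile the wording with the Exclusion Criteria in Section 2, which exclude women whose procedure requires overnight admission, including because of intraoperative complications. The two passages must describe one population.
2. **Sample size wording (Section 4).** Say that a missed visit is not in itself loss from the primary analysis. The planned 47 need not change.
3. **Contact (Section 3 and Post-operative Follow-up).** Ask the outside-care question by telephone at about 6 weeks of any woman who misses the visit. This also delivers what Aim 1 promises.
4. **Sensitivity analysis (Section 4).** Report the primary proportion again with women still unreached counted as events.

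The cost is one or two extra calls at the plan's no-show rate, about five at the assumed 10%, plus wording. The downside is that the reported event rate may be slightly higher.
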